4.6. Study Procedures and Flowchart

The study design is summarized in the flow chart below. Reference Protocol Schedule of Assessments (Tables 2 and 3) for the complete Schedule of Activities.

Figure 1. Study Design

Screening Day -28 to		Treatment Period Day 1	Follow-up Pe Day 2 to Da	
Clinic Assessments Day -28 to Day -8	Remote Assessments Day -7 to Day -1			
	Daily Remote Assessment Reminder Day -7 to Day -1		Daily Remote Assessment Reminder Day 2 to Day 6	
		Clinic Treatment Visit Day 1	Safety Phone Call Day 4	End Stud Visi Day

5. **Endpoints**

5.1. **Primary Endpoint**

Incidence of treatment-emergent adverse events (TEAEs)

5.2. **Secondary Endpoints**

- Change from baseline to Hour 6 of infusion in VAS-L ratings
- Change from baseline to Hour 6 of infusion in VAS-A ratings
- Change from baseline to post-infusion in VAS-L ratings measured via daily diary over multiple
- Change from baseline to post-infusion in VAS-A ratings measured via daily diary over multiple

•	•	Change from baseline in vital signs, electrocardiogram (ECG), and clinical laboratory parameters

Sponsor: Sage Therapeutics, Inc.; Protocol No.: 547-TRM-201

6. Analysis Sets

Details on the process for defining analysis datasets are located in the Data Review and Definition of Analysis Sets SOP (3911).

6.1. Screened Set

The Screened Set will include all participants who were screened for participation in this study.

6.2. Enrolled Set

The Enrolled Set will include all participants who provided written informed consent and passed the inclusion and exclusion criteria for study participation. Screen failures will not be included in this set.

6.3. Efficacy Set

The Efficacy Set will be defined as all participants who received any amount of IP and have at least one post-baseline efficacy evaluation.

6.4. Safety Set

The Safety Set (SS) will include all participants who received any amount of IP. The SS will be used for all analyses of safety endpoints.

6.5. Protocol Deviations

Protocol deviations identified during the study will be captured in the Electronic Data Capture (EDC) system. Protocol deviation management at Syneos Health is detailed in Protocol Deviation and Noncompliance Management (3101.W02).

7. General Aspects for Statistical Analysis

7.1. General Methods

- Continuous variables will be summarized using the number of observations (n), mean, standard deviation (SD), median, minimum, maximum, first quartile (Q1), and third quartile (Q3). In addition, change from baseline values will be calculated at each time point and summarized descriptively.
- For categorical variables, descriptive summaries will include counts and percentages.
- All relevant participant data will be included in listings. All participants entered into the database will be included in participant data listings

7.2. Key Definitions

7.2.1. Baseline

For in-clinic assessments, baseline is defined as the most recent value immediately prior to the start of IP infusion. For remote daily assessments, baseline is defined as the average of all available preinfusion values per participant. Change from Baseline is defined as the measurement at each timepoint minus the Baseline value.

7.2.2. Study Day

Study Day is calculated relative to the start date of study treatment and defined as follows:

- The day of participant receiving the IP infusion is designated as Day 1.
- For visit days after Day 1, study day = visit date Day 1 date + 1.
- For visit days prior to Day 1, study day = visit date Day 1 date. Thus, study days for screening visits are negative numbers. There is no "Day 0".

7.3. Missing Data

All participants will be used in the analysis using all non-missing data available. No imputation process will be used to estimate missing data.

Dates missing the day, or both the day and month of the year will adhere to the following conventions to classify TEAEs and to classify prior and concomitant medications.

In general, listings will present the actual partial or missing values rather than the imputed values that may be used in derivation. In instances where imputed values will be presented, imputed values will be flagged.

7.3.1. Adverse Events (AE)

If an AE start date is completely missing, do not impute the date but consider it as a TEAE, unless the AE end date is before the initiation of treatment, in which case the AE will be considered prior.

For partial AE start dates:

- When the year is known but the month and day is unknown, then:
 - If the year matches the year of first dose and the end date (if present) is after first dose date, or AE is ongoing, then impute as the month and day of earlier date of (the first dose date + 1 day, last dose date).

Sponsor: Sage Therapeutics, Inc.; Protocol No.: 547-TRM-201

- If the year of AE onset < year of initiation of the treatment, then the month and day will be set to December 31st.
- If the year of AE onset > the year of initiation of treatment, then the month and day will be set to January 1st.
- If the year and month are known, but the day is unknown, then:
 - o If the year of AE onset = the year of initiation of the treatment and:
 - The month of AE onset = the month of initiation of the treatment, then the day will be set to the day of initiation of the treatment.
 - The month of AE onset < the month of initiation of the treatment, then the day will be set to the last day of month of the particular year.
 - If the month of AE onset > the month of initiation of the treatment, then the day will be set to the 1st day of month.
 - o If the year of AE onset < the year of initiation of the treatment, then the day will be set to the last day of month of the particular year.
 - o If the year of AE onset > the year of initiation of the treatment, then the day will be set to the 1st day of month.
- If the imputed AE onset date is after the AE stop date, then the onset date will be set to the stop date.
 - When the year and day are present and the month is missing, treat it as if the day is missing, and only year is present. Follow the imputation rules for "year is known, but the month and day is unknown."
 - When the year is missing, but the month and/or day is known, treat this date as missing; do not impute.
- 7.3.2. Dates in Disease History (Dates of diagnosis, current episode, first episode)
 - If the year is present and the month and day are missing, then the month and day will be set to January 1.
 - If the year and day are present and the month is missing, then the month will be set to January.
 - If the year and month are present and the day is missing, then the day will be set to the 1st day of month.

7.3.3. Prior and Concomitant Medications

For the partial start date of medication:

- If the year is present and the month and day are missing, then the month and day will be set to January 1.
- If the year and day are present and the month is missing, then the month will be set to January.
- If the year and month are present and the day is missing, then the day will be set to the 1st day of month.
- If the imputed start date of medication is after the end date (imputed date if applicable) of medication, then the start date will be set to the end date of medication.

For the partial end date of medication:

- If the year is present and the month and day are missing, then the month and day will be set to either December 31 or date of death, whichever is earlier.
- If the year and month are present and the day is missing, then the day will be set to the last day of the month or month of death.

Sponsor: Sage Therapeutics, Inc.; Protocol No.: 547-TRM-201

• If the year and day are present and the month is missing, then treat it as if the day is also missing. Set the month and day to be either December 31 or date of death, whichever is earlier.

7.4. Visit Windows

There will be no windowing for visits.

7.5. Pooling of Centers

Not applicable.

7.6. Subgroups

No subgroup analysis is planned for this study.

8. Demographic, Other Baseline Characteristics and Medication

8.1. Participant Disposition and Withdrawals

The summaries of participant disposition will include the number and percentages of participants who were screened, screen failed, treated, completed treatment, discontinued IP prematurely with primary reasons for discontinuing IP, completed the study, and prematurely withdrew from the study with primary reasons for not completing the study. All percentages will be calculated based on the participants who were enrolled, unless otherwise stated. If a participant is rescreened because the participant has been a screen failure the first time, the status of the participant will be determined from the second screening. In the count of screened participants, such a participant will be counted only once. Participants of all analysis sets will be summarized (eg, number and percentages of participants in Screening Set, Enrolled Set, Efficacy Set, and Safety Set)..

A listing will be provided for participants screen failed with primary reason and a disposition listing will be provided for all enrolled participants. A separate listing will be provided for the Safety Set and reported for participants who prematurely discontinued IP, prematurely withdrew from the study with reasons, and date of withdrawal from the study.

8.2. Protocol Deviations

All major protocol deviations will be summarized using the Safety Set. All protocol deviations (major and minor) will be included in a data listing for the Enrolled Set.

Any violation of inclusion/exclusion criteria will also be presented in a separate data listing using the Screened Set.

8.3. Demographic and Baseline Characteristics

Demographic data including age, sex, race, ethnicity, and baseline characteristics (e.g., weight, height, BMI, childbearing potential), will be summarized and listed using the Safety Set. The below conversions will be used if needed.

Body mass index (BMI) (kg/m²) = Weight(kg)/[Height(m)²]

8.4. Medical History

Medical history collected at screening will be analyzed using the Safety Set and coded using the Medical Dictionary for Regulatory Activities (MedDRA) terminology. The summary will be presented by primary system organ class (SOC) and preferred term (PT). A participant will be counted once within each level of summarization. Medical history will be presented in a corresponding listing.

8.5. Tinnitus Medical History

Tinnitus medical history will be analyzed for the Safety Set and will include at a minimum information related to initial onset, tinnitus pulse, perception, loudness, sound, awareness, conditions that worsen symptoms, hearing aid use, and sound tolerability. Tinnitus medical history will be tabulated and a corresponding listing provided.

8.6. Prior and Concomitant Medications

Medications will be recorded throughout the duration of the study and will be coded using World Health Organization (WHO) Drug Dictionary Global B3 September 2022, or later.

Medications taken prior to the initiation of the start of IP will be denoted "Prior". Those medications taken prior to the initiation of the IP and continuing beyond the initiation of the IP, or those medications started at the same time or after the initiation of IP will be denoted "Concomitant".

Both prior and concomitant medications will be separately summarized by anatomical therapeutic chemical (ATC Level 3) class and preferred term. Note that medication taken before the initial dosing of the IP and continued after the initial dosing will be categorized as a prior medication and, separately, as a concomitant medication. All prior and concomitant medications will be listed. Medications will be presented according to whether they are "Prior" or "Concomitant", as defined above. If medication dates are incomplete and it is not clear whether the medication was concomitant, it will be assumed to be concomitant. Missing date imputation rules are provided in Section 7.3.3.

Concomitant procedures are recorded on a separate electronic case report form (eCRF) page; this will be presented in a listing by participant.

The Safety Set will be used for all tables and listings.

8.7. Extent of Exposure

The number and percentage of treated participants receiving 6 hours of infusion will be tabulated. Detailed information regarding the infusion timepoints, planned doses, actual infusion rates, infusion interruptions, infusion discontinuations, and dose changes will be listed for each participant in the Safety Set.

Study drug exposure will be summarized using actual infusion duration, dose changes, infusion rate changes, and interruptions lasting more than 5 minutes. Actual infusion duration is the elapsed time between start time and stop time of study drug administration, defined as stop time (HH:MM) – start time (HH:MM), and will not include any dose interruptions lasting more than 5 minutes. Actual cumulative infusion duration is the sum of all actual infusion durations. The total length of interruption is the elapsed time between end time of one infusion and the start time of the next recorded infusion.

Detailed information regarding the infusion timepoints, planned dose, actual infusion rate, infusion interruption, and permanent infusion discontinuation will be listed for each participant in the Safety Set by timepoint. Actual cumulative infusion duration and cumulative length of infusion interruption lasting more than 5 minutes will be tabulated, along with number of unique infusion interruptions among treatment completers.

8.8. Treatment Compliance

The planned dose of 30, 60, or 90 mcg/kg/hour will be captured in the EDC system. The actual infusion rate will also be captured in the EDC in mL/hour, and converted to actual dose mcg/kg/hour using the following formula:

1000 mcg/hour * (actual flow rate from infusion pump in mL/hour) / (participant weight in kg)

Treatment compliance will be calculated as:

(actual dose / planned dose) * 100

Planned dose, actual infusion rate, actual dose, and percent compliance will be listed for each participant in the Safety Set by timepoint. Overall treatment compliance will be tabulated.

9. Efficacy

All efficacy analyses will be based on the Efficacy Set.

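### The interruption count covers only undefined treatment completers, and the compliance ratio has no duration term (minor; descriptive tables only)

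*SAP*

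**What the plan says.** **Interruptions (SAP 8.7, Extent of Exposure).** The SAP tabulates cumulative infusion duration and cumulative length of interruptions over 5 minutes, together with the "number of unique infusion interruptions among treatment completers". The same section has broader outputs: "Study drug exposure will be summarized using actual infusion duration, dose changes, infusion rate changes, and interruptions lasting more than 5 minutes", and "The number and percentage of treated participants receiving 6 hours of infusion will be tabulated". Infusion duration "will not include any dose interruptions lasting more than 5 minutes". Interruptions and permanent discontinuations are listed for every participant in the Safety Set.

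No definition of a treatment completer appears. SAP 8.1 uses completed treatment as a disposition category without criteria. Protocol 7.6 defines only completion of the study, through the End of Study Visit.

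**Compliance (SAP 8.8, Treatment Compliance).** The denominator is a rate: "The planned dose of 30, 60, or 90 mcg/kg/hour will be captured in the EDC system". The numerator is the pump flow in mL/hour, converted to mcg/kg/hour by "1000 mcg/hour * (actual flow rate from infusion pump in mL/hour) / (participant weight in kg"). Compliance is then "actual dose / planned dose) * 100", listed by timepoint, and "Overall treatment compliance will be tabulated". The section does not say how timepoints are combined, or what happens to timepoints after a permanent stop.

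**The concern.** The primary objective is safety and tolerability, and SAP section 12 expects only about 10 participants to be dosed. Each descriptive table therefore rests on very few people, and readers will take its label at face value.

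- **Interruptions.** Limiting the count to completers selects on something that happens after the interruption. The person most likely to be left out is one whose infusion was paused, restarted and then ended early.
- **Compliance.** A ratio of two rates shows whether the pump ran at the intended speed. It does not show how much of the infusion was given. Under the name treatment compliance, a value at or near 100% can stand beside a small fraction of the planned dose.
- **Units (editorial).** The constant in the conversion formula is written in mcg/hour, which does not yield mcg/kg/hour.

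**Working it through.** The documents state no compliance figure and no planned total dose, so there is no sponsor figure to reproduce.

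**Step 1: planned total.** Inputs are from SAP 4.5 Table 1 (same schedule in Protocol 10.5 Table 5): 30 mcg/kg/hour for 0 to 0.5 h, 60 for 0.5 to 1 h, and 90 for 1 to 6 h.

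30 × 0.5 + 60 × 0.5 + 90 × 5 = 15 + 30 + 450 = 495 mcg/kg.

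**Step 2: early stop at planned rates.** For a stop at hour s (s ≥ 1), the delivered dose is 45 + 90 × (s − 1). The rate ratio at each recorded timepoint is planned/planned × 100 = 100%.

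| Stop | Delivered (mcg/kg) | % of 495 | Rate ratio at each recorded timepoint |
|---|---|---|---|
| just after 1 h | 45 | 9.1% | 100% |
| 2 h | 135 | 27.3% | 100% |
| 3 h | 225 | 45.5% | 100% |
| 4 h | 315 | 63.6% | 100% |
| 5 h | 405 | 81.8% | 100% |

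**Step 3: overall figure under two possible rules.** Take the stop at Hour 2.

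- Rates recorded on the three steps of Table 1 and averaged: (100 + 100 + 100)/3 = 100%. The same holds for any stop after Hour 1.
- Assumed alternative, with seven timepoints (0, 0.5, 1, 2, 3, 4 and 5 h) and those from the stop onward scored 0: 3 × 100/7 = 42.9%.

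The same infusion gives 100% or 42.9%, and the SAP does not say which rule applies.

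**Step 4: an omitted interruption (assumed pattern).** SAP 4.5 and Protocol 7.4 allow a pause for sedation, a restart, and no restart after confirmed hypoxia. Suppose a pause from 2 to 2.5 h, a restart at 90, and a final stop at 4 h.

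- Delivered: 135 + 90 × 1.5 = 270 mcg/kg, and 270/495 = 54.5%.
- Rate ratio: 100% at each infused timepoint.
- Completer count: the pause is absent, because treatment was not completed.
- Cumulative interruption length: the 0.5 h is still tabulated, provided the completer limit applies only to the count, which is the natural reading of the sentence.

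With about 10 dosed, one such participant is 1/10 = 10% of the sample missing from that row. A single stop with no restart removes nothing from a count of interruptions.

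**Step 5: why delivered dose should not be called compliance.** With a permitted reduction to 60 at Hour t, the delivered dose is 45 + 90(t − 1) + 60(6 − t).

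- t = 1: 345, or 69.7%.
- t = 3: 405, or 81.8%.
- t = 5: 465, or 93.9%.

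A reduction at Hour 3 and a stop at Hour 5 both deliver 405 mcg/kg, so the percentage alone cannot tell them apart.

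**Step 6: units.** (mcg/hour) × (mL/hour) / kg = mcg·mL/(hour²·kg). With a concentration instead, (mcg/mL) × (mL/hour) / kg = mcg/kg/hour. Protocol 10.1 gives only the undiluted strength, 5 mg/mL, and says the product must be diluted. The value 1000 therefore cannot be confirmed from the documents.

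**The case against.** The strongest reply is that the SAP separates rate from duration on purpose and reports both. For an infusion run by site staff, checking the pump rate in 8.8 and the infused time in 8.7 is defensible. Early stops show in the count of participants receiving 6 hours, in cumulative duration and in disposition. Interruptions show in the unrestricted exposure summary, the cumulative interruption length, the Safety Set listings and the tables of TEAEs leading to interruption (SAP 10.1.1). Sedation-related interruptions also appear in the AESI summary (SAP 10.1.2). All of this stands, and it keeps the point minor.

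It also rules out several stronger readings that a reader might infer:

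- *Early stops will be reported as 100% compliant overall.* Not established. The aggregation rule is unstated and may be in the table shells, which SAP section 15 places in separate documents.
- *Interrupted participants disappear from the report.* They are missing from one row, not from the outputs named above.
- *A completer must have 6 net hours, so people who paused and finished are dropped too.* Nothing links the term to the 6-hour count. SAP 8.1 sets completed treatment beside premature discontinuation, which points to the ordinary meaning.
- *The tolerability assessment itself is conditioned on tolerating the infusion.* The count sits under exposure. Tolerability is evaluated through TEAEs in the Safety Set.
- *Percentage of 495 mcg/kg should replace compliance.* That would score pauses and stops directed by the documents as non-compliance.

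The reply does not answer three things: the completer restriction has no stated purpose or definition, the label in 8.8 promises more than a rate ratio delivers, and the rule for the overall figure is missing from the SAP.

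**Conclusion.** The point holds as a minor one, confined to descriptive tables. No endpoint and no model uses these quantities.

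- **Certain from the text:** SAP 8.8 has no duration term, so an early stop at planned rates gives 100% at every recorded timepoint. Treatment completer is undefined. The unit of the conversion constant is wrong.
- **Conditional:** an overall value of 100% with 9.1% or 27.3% of the planned dose delivered requires averaging over recorded timepoints or over the three rate steps. The omission of people paused, restarted and later stopped assumes that completer means completed treatment as in SAP 8.1.
- **Unknown:** how often interruptions or early stops will occur. The documents give no rate. In a trial of about 10, one case would change the row visibly.

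**What to change.** 1. **SAP 8.7, interruption count.** Delete the completer restriction and tabulate the number of unique interruptions for the whole Safety Set. Add a completer row only if the term is defined.
2. **SAP 8.8.** Rename the measure infusion-rate adherence, keep it by timepoint, and state how timepoints are combined and how those after a permanent stop are handled.
3. **SAP 8.7, exposure.** Add cumulative delivered dose, the sum of actual rate × infused time with pauses over 5 minutes excluded as 8.7 already does, as a percentage of 495 mcg/kg. Present it as exposure, not compliance. Show protocol-permitted reductions and protocol-directed pauses or stops separately, so that they are not read as non-compliance.
4. **Editorial.** Give the conversion constant in mcg/mL and confirm the value 1000 against the pharmacy manual.

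The cost is SAP wording and slight extra programming. Rates, infusion times and interruptions are already captured, so data collection and dosing do not change. The drawback is that delivered dose mixes rate with duration and may look less favourable than the present ratio, which is why the rate measure stays beside it.

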9.1. Visual Analog Scales

The VAS-L and VAS-A are participant-rated scales for evaluating tinnitus (Adamchic et al 2012). Scoring for both is along a linear horizontal scale, with the left side anchor (score of 0) representing the lowest severity and the right side anchor (score of 100) representing the highest severity of the rated tinnitus experience. Intermediate scores are determined by extrapolation between the two sides of the scales.

To assess tinnitus loudness (VAS-L), participants will answer the question "How loud is your tinnitus now?" on a horizontal scale anchored on left by "not audible" and on right by "extremely loud". To assess tinnitus annoyance (VAS-A), participants will answer the question "How much is your tinnitus annoying you now?" on a horizontal scale anchored on left by "not annoying" and on right by "extremely annoying".

The VAS-L and VAS-A will be administered both as remote and as in-clinic measures at different times of this study. Remote VAS data collection will occur from Day -7 to Day -1 (preinfusion) and from Day 2 to Day 7 (postinfusion). For remote assessments, ratings for both VAS-L and VAS-A will be obtained twice daily, once each in the morning and once in the evening. And the daily arithmetic means of VAS-L and VAS-A ratings will be computed separately for remote measures obtained during pre- and postinfusion periods. -. For remote assessments, the daily arithmetic mean will be calculated by averaging the morning and evening scores ([morning score + evening score] / 2). If a participant is missing either a morning or evening score, then the single available score will be used as the mean for that day.

The VAS-L and VAS-A will be obtained in-clinic during the treatment period (Day 1), administered once prior to start of infusion and then repeated at hours 0.5, 1, 2, 3, 4, 5 and 6 of the infusion.

For the treatment period (Day 1), baseline is defined as the most recent value immediately prior to the start of IP infusion, or predose. For the postinfusion remote assessment period (Days 2 through 7), baseline is defined as the average of all available preinfusion values per participant collected from Day -7 through Day -1. This will be calculated by summing the daily arithmetic means and dividing by the total number of non-missing days. If a participant is missing either a morning or evening score, then the single available score will be used as the mean for that day Missing day or partial missing day VAS ratings will not be imputed.

Descriptive statistics of both VAS component scores and VAS component change from baseline scores will be tabulated. Considering the small sample size, unbiased Hedge's g will be used to compare the effect size of the post baseline score at each timepoint to the baseline score. Hedge's g will be calculated for pre-post scores in one group using the following formula:

$$g = d \times J$$
 Where $d = \frac{(post-baseline\ mean)-(baseline\ mean)}{SD_{within}}$ and $J = 1 - \frac{3}{4(2n-2)-1}$

SD_{within} can be computed from the standard deviation of the change from baseline (SD_{CFB}) as

$$SD_{within} = SD_{CFB}/\sqrt{2(1-r)},$$

r is the correlation between baseline and post-baseline, n is the number of pairs.

The 95% CI of Hedge's g will be calculated as

$$g \pm t(n-1, 0.025) \times SE(g);$$

Where
$$SE(g) = \sqrt{Var(g)} = \sqrt{Var(d)} \times J^2 = \sqrt{\left(\frac{1}{n} + \frac{d^2}{2n}\right)2(1-r)} \left(1 - \frac{3}{4(2n-2)-1}\right)^2$$

(Borenstein et al 2009).

[figure not shown]
Each VAS component score will be analyzed separately; this will also be done separately for Day 1 (during treatment) and Days 2 to 7 (after treatment).

For each component, a mixed-effects model for repeated measures will be considered. Each repeated measures model will include (a) change from baseline scores as the dependent variable and (b) both baseline VAS component value and visit as fixed effect independent variables. The residual errors from the same participant across visits will be modeled using an unstructured covariance matrix (UN). If the model using an unstructured covariance matrix does not converge, compound symmetry (CS) and first order autoregressive (AR(1)) covariance structures may be used, in that order. Model-based point estimates (i.e., least squares means, their 95% confidence intervals (CIs), and standard errors (SEs) will be reported. For Day 1 the repeated timepoint will be hours and for Days 2 through 7 the repeated timepoint will be days.

Example SAS code:

Line plots of least squares (LS) mean will be plotted with standard error bars. Q-Q plot for residuals will also be provided to assess normality assumptions.

Listings of observed raw scores and change from baseline values will be presented separately for each VAS component by participant.

_	

	_
	_
	4
	-
	_
	ı
	i
	
	_
	_
	-
	-

10. Safety

The Safety Set (SS) will be used for all safety analyses. Safety and tolerability of brexanolone will be evaluated by incidence of treatment-emergent adverse events

Listings for discharge and safety phone call will also be included.

